## 825 **SPECIFIC AIMS AND HYPOTHESES:**

826 **Aim 1: To confirm that PM women with histories of recurrent DEP will, at baseline, suffer**  
827 **from greater CV risk relative to never DEP PM women, and to examine the role of**  
828 **cumulative trauma exposure in the relationship of history of recurrent DEP and CV risk.**

829

830 **H1:** When compared with never DEP women, women with histories of recurrent DEP will  
831 exhibit a greater Stress Reactivity composite score. If confirmed, the following parallel  
832 secondary hypotheses will be examined in hierarchical order: Women with histories of recurrent  
833 DEP will exhibit: 1) an increased rate of metabolic risk; and 2) reduced endothelial flow-  
834 mediated dilatation and baroreceptor sensitivity.

835 **H2: Secondary Hypothesis:** Cumulative trauma exposure will moderate the relationship between  
836 histories of recurrent DEP and CV risk such that greater trauma exposure will explain part of the  
837 relationship between DEP history and elevated CV risk (tested with sensitivity analyses).

838 **Aim 2: To examine progression in CV risk and affective well-being over 12 months in**  
839 **untreated PM women as a function of histories of DEP.**

840 In the 160 women randomized to placebo we will test the following hypotheses by comparing  
841 women with a history of DEP with never depressed women for changes over 12 months:

842 **H1:** Relative to baseline reactivity, untreated women with a history of DEP will show a greater  
843 increase in the Stress Reactivity composite score over 12 months compared with never DEP  
844 women. If confirmed, the following parallel hypotheses will be examined in hierarchical order:  
845 In women with a history of DEP: 1) there will be a greater increase in rate of metabolic risk; and  
846 2) a greater reduction in endothelial flow-mediated dilatation and baroreceptor sensitivity.

847 **H2:** A greater proportion of untreated women with a history of DEP will exhibit episodes of  
848 DEP over 12 months compared with untreated women without a history of DEP. If confirmed,  
849 the following parallel hypotheses will be examined in hierarchical order: Untreated women with  
850 a history of DEP will have 1) higher CES-D DEP scores; 2) increased functional impairment;  
851 and 3) increased affective instability (greater variance in CES-D over 12 months).

852 **Aim 3: To examine predictors and mediators of ERT- related treatment efficacy for**  
853 **affective well-being and CV risk.**

854 In the 320 women randomized to treatment we will test the following hypotheses:

855 **H1A:** Women on active treatment will show a decreased Stress Reactivity composite score over  
856 12 months relative to baseline levels and relative to the change (increased stress reactivity) in  
857 women on placebo. If confirmed, the following parallel hypotheses will be examined in  
858 hierarchical order: Women on active treatment will show 1) a lower rate of metabolic risk; and 2)  
859 increased endothelial flow-mediated dilatation and baroreceptor sensitivity. These hypotheses  
860 will be tested as main effects of treatment.

861 **H1B:** A history of DEP will predict a greater effect of ERT on Stress Reactivity: i.e., a greater  
862 decrease in Stress Reactivity (relative to baseline) between active and placebo treated women  
863 will be seen in women with a history of DEP (due to their higher baseline reactivity) compared  
864 with never DEP women. If confirmed, the following parallel hypotheses will be examined in  
865 hierarchical order: a history of DEP will predict a greater effect of ERT for 1) reductions in rate  
866 of metabolic risk, and 2) increased endothelial flow-mediated dilatation and baroreceptor  
867 sensitivity. These hypotheses will be tested as interactive effects (history by treatment).

868 **H2:** Although no subjects will be depressed at baseline, active treatment will be associated with  
869 a lower proportion of women experiencing episodes of DEP over 12 months relative to placebo  
870 treated women. If confirmed, the following parallel hypotheses will be examined in hierarchical  
871 order: Active treatment will be associated with: 1) lower CES-D DEP scores; 2) decreased  
872 functional impairment; and 3) decreased affective instability.

873 **H3: Secondary Hypothesis:** Treatment-related reductions in Stress Reactivity will partially  
874 mediate the beneficial effect of E2 on DEP episodes. If confirmed, the following parallel  
875 hypotheses will be examined in hierarchical order: Treatment reductions in Stress Reactivity will  
876 partially mediate reductions in 1) CES-D DEP rating scores; 2) Functional Impairment; and 3)  
877 Affective Instability (tested with sensitivity analyses).

878 **DATA ANALYTIC PLAN FOR EACH HYPOTHESIS**

879 **Aim 1 Hypothesis 1:** Since subjects have not yet been assigned to treatment, we will treat  
880 analyses of baseline data as two-group analyses rather than a main effect in a two-by-two  
881 factorial. The Stress Reactivity composite score as the response. If the null hypothesis is  
882 rejected, we will examine the same contrast for metabolic risk (as a parallel logistic regression  
883 model since it is categorical), flow mediated dilatation, and baroreceptor sensitivity.

884 **Aim 1 Hypothesis 2:** This secondary analysis will add the effect of trauma to the model, and  
885 assess whether trauma moderates the effect of DEP history on CV risk variables (above).

886 **Aim 2 Hypothesis 1:** In the mixed random coefficients model we will use for this repeated  
887 measures analysis, we will test this hypothesis using a contrast that examines the difference  
888 between the women with and without histories of DEP on the difference between the month 0  
889 and month 12 least squares means. This contrast will be done in the context of the full model but  
890 involves means from 2 of the 4 between-subjects cells. If this null hypothesis is rejected, we will  
891 test the same hypotheses for flow mediated dilatation and baoreceptor sensitivity (mixed model),  
892 and examine metabolic risk (categorical) via parallel logistic regression model.

893 **Aim 2 Hypothesis 2:** We will fit a two-factor logistic regression predicting the presence or  
894 absence of DEP episodes during the follow-up period. If we reject the null hypothesis, we will  
895 follow this with a two-factor mixed random coefficient model using CED-D, functional  
896 impairment and (using without the repeated measures portion since affective instability is  
897 defined over the entire follow-up period) affective instability as defined earlier. Further, as  
898 sensitivity analyses, we will examine the same effect on number of episodes / month during the  
899 follow-up period, using Poisson regression, and on the CES-D scores themselves using a mixed  
900 model.

901 **Aim 3 Hypothesis 1 (A and B):** With stress reactivity as the response, we will test these  
902 hypotheses in the context of the two between-factor one-repeated factor mixed random  
903 coefficient model we listed earlier. Hypothesis H1A is the main effect for treatment, predicting  
904 that the difference between the change in LSMs from month 0 to month 12 will be in different  
905 directions in the treated and untreated women. If this null hypothesis is rejected, we will examine  
906 parallel effects on metabolic risk (via a logistic regression), baroreceptor sensitivity, and flow  
907 mediated dilatation. Hypothesis H1B involves partitioning the interaction effect in these models.

908 **Aim 3 Hypothesis 2:** This will be examined in a logistic regression model with two between-  
909 subjects factors (DEP history and treatment) and the emergence of at least one DEP episode as  
910 the response. This is the treatment main effect in the model. If we reject the null hypothesis, we  
911 will examine the same hypothesis using CED-D total (mixed model), functional impairment  
912 (mixed model), number of episodes (Poisson regression), and affective instability (mixed model).

913 **Aim 3 Hypothesis 3 (secondary):** This hypothesis will use a logistic regression model with two  
914 between-subjects factors as above, the emergence of at least one DEP episode as the response,  
915 and stress reactivity in the model as a mediator.

916

917 **POWER AND SAMPLE SIZE CALCULATIONS FOR EACH SPECIFIC AIM:**

918 It is not feasible to conduct power analyses for every hypothesis. While this is a mechanistic  
 919 study designed, in part, to examine mediators of E2's beneficial effects on CV risk and DEP, we  
 920 must first be able to detect a beneficial effect of E2. Thus, we conduct power for Aim 3, H2.  
 921 We also felt it important, however, to confirm we are powered to detect meaningful differences  
 922 in the Stress Reactivity composite score since it is our primary CV outcome variable and also a  
 923 predicted mediator.

924 **Aim 3 Hypothesis 2:** Based on the work of Freeman et al (Menopause, 2009. **16**(4): p. 728-34)  
 925 for rates in untreated women, and our prediction that ERT will cut the rate of depression by 50%  
 926 (a clinically relevant difference), we predict the following percentages of women will experience  
 927 at least one DEP episode during the follow-up in our groups:

928

		Treatment Assigned	
		ERT	Placebo
Depression	Positive	22.5	45
History	Negative	15	30
(Combined)		(18.75%)	(37.5%)

929

930 The hypothesis corresponds to using logistic regression to test the depressive episode rate  
 931 between all those treated with ERT (18.75%) versus those treated with placebo (37.5%). Using a  
 932 logistic regression with this effect size, a two-tailed significance level of 0.05, and 240 total  
 933 subjects, power exceeds 96%. Further, power should be higher for the parallel poisson  
 934 regression on number of episodes, and for the analysis of the CES-D scores themselves.

935 **Aim 1, H1:** Our primary hypothesis for Aim 1 involves Stress Reactivity and since we cannot  
 936 assert that any stress-responsive factor is more important than another in this context, we will  
 937 combine different measures of stress-responsive CV risk factors and combine them into an index  
 938 called Stress Reactivity, described above. Since this measure has not been used before, we do  
 939 not have information from prior research on means and standard deviations which could help  
 940 with power and sample size calculations. Instead, we performed power calculations for each of  
 941 the stress reactivity variables which comprise the composite score. We used differences between  
 942 DEP and non-DEP groups from Pace et al. (Am J Psychiatry, 2006. **163**(9): p. 1630-3) for IL-6;  
 943 from Young et al. (Neuropsychopharmacology, 2000. **23**(4): p. 411-8) for cortisol; from  
 944 Brownley et al. (Am J Obstet Gynecol, 2004. **190**(4): p. 1052-8) for clinically relevant  
 945 differences in MAP; and from [name] (Health Psychol, 2007. **26**(2): p. 201-13; Int J  
 946 Psychophysiol, 1994. **17**(3): p. 233-48).for group differences in VRI – using the reported group  
 947 differences to define the magnitude of differences which are important, and to obtain estimates  
 948 of SDs. We obtained effect sizes of 0.63, 0.86, 1.0, and 1.5 for differences in delta MAP, VRI,  
 949 IL-6, and Cortisol, respectively. Our sample size of 160 per DEP group yields **99% power to**  
 950 **reject a null hypothesis** of no effect for an effect size of 0.63, (the smallest above), and 80%  
 951 power to detect an effect size as small as 0.40. Due to the complexity of the random coefficient

952 model to be used for this variable, we approximated our calculations with a simpler ANOVA  
953 power on change scores. Our actual power should be higher because the model should be more  
954 precise.

955 **Inducements for Participation**

956 Total possible monetary inducement for participating = \$1,275, prorated as follows:

957 \$100 for the medical and psychiatric screening (these screenings also provide benefit in the form  
958 of free medical evaluations)

959 \$150 for each laboratory test session (\$450 total)

960 \$100 for each flow mediated dilatation procedure (\$300 total)

961 \$ 25 for each interim study visit (\$125 total)

962 \$300 compliance bonus for completing the study in full compliance

963

964

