- 34 • If a participant knew the complete family history for the mother's side but none or only  
35 partial history for the father's side, it was decided that the study gynecologist would evaluate  
36 whether transdermal estradiol would be contraindicated based on the history provided – if  
37 not, she could enter the trial **(2012-09-20)**.
- 38 • Women with a single episode of past depression were considered eligible if their single  
39 episode met the following criteria: the duration was at least 3 months, at least 6 of 9 MDD

- 40 symptoms were experienced (exceeding the required 5-symptom threshold), and the episode  
41 occurred as an adult (not in childhood or early adolescence) **(2013-08-05)**.
- 42 • The acceptable age range extended from 45-55 to 45-60 **(2014-02-27)**.
  - 43 • The exclusion criteria related to psychiatric history were changed to exclude women with:  
44 history of suicide attempts; history of bipolar and related disorders or schizophrenia  
45 spectrum and other psychotic disorders; history of severe substance use if it was in the past  
46 10 years; less than two years in remission from substance use disorders, bulimia nervosa,  
47 anorexia nervosa, or posttraumatic stress disorder; current psychiatric diagnosis of binge  
48 eating disorder, a neurodevelopmental disorder, or a trauma- and stress-related disorder  
49 (except for posttraumatic stress disorder) with severity greater than mild **(2014-02-27)**.
  - 50 • Women having had a bilateral oophorectomy were allowed into the trial if the procedure had  
51 occurred within 24 months and the participant had been menstruating regularly prior to the  
52 procedure **(2014-02-27)**.
  - 53 • The requirement of having a baseline CES-D score  $\leq 8$  was increased to  $\leq 16$  **(2010-11-16)**  
54 and later removed altogether **(2014-02-27)**.
  - 55 • The acceptable body mass index range was lowered to  $<30$  due to concerns that estradiol  
56 therapy may be less safe in obese women **(2011-08-18)** but was later increased to  $<35$  based  
57 on research suggesting that transdermal estradiol, specifically, was not related to an  
58 increased health risk in these women **(2014-04-04)**.

59

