## 198 **Inclusion Criteria**

- 199 • Natural perimenopause ( $\geq 2$  skipped cycles and an interval of amenorrhea  $\geq 60$  days with  
200 FSH  $> 2$  SD above mean premenopausal levels)
- 201 • 45 – 55 years of age
- 202 • Normal mammogram within one year of study entry
- 203 • Normal breast, pelvic and endometrial exam
- 204 • Current low level depressive symptoms (CES-D score  $< 8$ )

- 205 • Five or more years in remission from any anxiety disorders, substance abuse, or eating  
206 disorders.  
207

208 **General Exclusion Criteria:**

- 209 • Endometrial hyperplasia (confirmed by endometrial ultrasound and/or biopsy)  
210 • Abnormal uterine anatomy (e.g. fibroids)  
211 • History of thrombophlebitis or thromboembolic disorders  
212 • History of estrogen-dependent neoplasias  
213 • Gall bladder disease  
214 • Liver dysfunction or other disorders for which estrogen or progesterone use is  
215 contraindicated  
216 • History of any CVD including coronary artery disease, arteriosclerosis, heart attack, or  
217 stroke  
218 • Atrial fibrillation, frequent premature atrial or ventricular beats, or other rhythm  
219 abnormalities  
220 • Type I or Type II diabetes  
221 • Known sensitivities to any ingredient in the Climara® transdermal estradiol system or  
222 Prometrium® (oral micronized progesterone)  
223 • Stage 1 or 2 hypertension (SBP  $\geq$  140 mmHg or DBP  $\geq$  90 mmHg)  
224 • Fasting low density lipoprotein (LDL) levels  $\geq$  190 mg/dl  
225 • BMI  $>$  37  
226 • Use of psychotropics, antihypertensives, statins, or hormonal preparations, or frequent  
227 use of anti-inflammatory agents ( $>$  10 times/month).  
228 • Use of herbals indicated for menopausal symptoms (e.g. black cohosh) and/or mood (e.g.  
229 St. John's Wort). Other herbals may be permitted if cleared by the study physicians.  
230 • History of suicide attempts  
231 • Current Axis I psychiatric diagnosis (e.g., depression, anxiety, substance  
232 abuse/dependence)  
233 • Less than five years in remission from any anxiety, substance abuse or eating disorder  
234 • History of substance dependence, bipolar or psychotic disorder  
235 • Current migraine with aura or a history of migraine with aura if less than 5 years prior to  
236 enrollment  
237 • Cigarette smoking  $>$  10 per day  
238 • Any history of migraine with or without aura in current cigarette smokers  
239

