### 314 **D.3. Procedures**

#### 315 **I. Screening Medical and Psychiatric Evaluations**

316 Following the informed consent process, subjects will complete a detailed medical and  
317 medication history form (enclosed); demographic data and height, weight and waist  
318 circumference will be obtained. Questionnaires assessing functional impairment, sleep quality  
319 and climacteric symptoms, diet and physical activity level will be administered (enclosed). The  
320 CES-D scale will also be administered. CES-D scores  $\geq 9$  will result in exclusion and referral  
321 for further evaluation. Stethoscopic BP will also be taken. Using JNC 7 guidelines, women  
322 exhibiting Stage 1 or Stage 2 hypertension (HTN) (140+ mmHg SBP and/or 90+ mmHg DBP)  
323 will be excluded and referred. Women will also have a fasting blood draw to determine FSH,  
324 plasma lipids (HDL-C, LDL-C, and triglycerides), and fasting glucose. As per the National  
325 Cholesterol Education Program (NCEP) and American Diabetes Association guidelines, fasting  
326 LDL  $\geq 190$  mg/dl or fasting glucose  $\geq 7.0$  mmol/l (126 mg/dl) (exclusionary) will prompt a  
327 referral. See A.4.8. for monitoring of change in health status during the course of the study.

328

329 Subjects meeting medical and psychiatric screening criteria will have a psychiatric evaluation  
330 with clinical psychologist [name], who will administer the Structured Clinical Interview for  
331 DSM-IV (SCID-NP with psychotic screen) for Axis I disorders and who will administer the  
332 cumulative trauma interview. Any woman meeting criteria for a current Axis I disorder will be  
333 excluded and referred for treatment. Women meeting psychiatric inclusion criteria will be  
334 scheduled for a gynecological exam with [name] who will take a complete medical history,  
335 including a history of estrogen-dependent neoplasia, a history of thrombophlebitis or  
336 thromboembolic disorders, gall bladder disease, liver dysfunction or other disorders for which  
337 estradiol or progesterone use is contraindicated. He will also perform a pelvic exam as well as  
338 endometrial ultrasound to confirm that they are free of any signs or history of endometrial  
339 disorder, abnormal uterine anatomy (e.g. fibroids), abnormal ovarian anatomy (e.g.  
340 endometrioma). If the endometrium is  $> 4$  mm, a routine endometrial biopsy will be performed  

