### 535 **Affective Well-Being Measures**

536 **1. Depression Episodes** will be operationalized in a manner consistent with other studies in  
537 perimenopausal depression and based on the following assessments: **The Center for**  
538 **Epidemiologic Studies Depression scale (CES-D)** is a 20-item self-report form assessing  
539 depressed mood. CES-D scores  $\geq$  16 have been consistently validated as defining high  
540 depressive symptoms suggestive of clinically significant DEP (positive predictive value=75%),  
541 and this cut-point has been used to define depressive episodes in multiple perimenopausal  
542 samples. Moreover, elevated CES-D scores have been shown to be sensitive to the anti-  
543 depressant actions of ERT in PM women. **Thus, CES-D scores  $\geq$  16 will be used to**  
544 **operationally define ‘depression episodes’.** However, if CES-D scores are  $>$  10 at any study  
545 visit then the Structured Clinical Interview for DSM-IV (non-patient edition) will be

546 administered to determine the presence of either minor or major depression. **Functional**  
547 **Impairment:** We will use the widely used Medical Outcomes Study 36-item short form (SF-  
548 36), which yields scores of general health perceptions, physical functioning, role limitations due  
549 to physical functioning, social functioning, bodily pain, general mental health, role limitations  
550 due to emotional problems, and vitality. The rationale for the selection of this instrument is  
551 based on: 1) the demonstration that it is sensitive to change over time; 2) its incorporation of  
552 subscales to specifically assess functional impairment related to emotional and physical  
553 symptoms as well as overall social functioning; 3) its able to discriminate subgroups of CVD  
554 patients known to have poorer survival and worse disease; and 4) normative data for this scale  
555 are available for the general US population as well as 13 medical conditions. **Symptom**  
556 **Severity and Affective Instability** will be assessed with the CES-D scale (at baseline and  
557 months 2,4,6,8,10 and 12), the former with a repeated measures approach and the latter by the  
558 variance in the CES-D score over 12 months.

559 **Lifetime Trauma Exposure** will be assessed by a validated interview. A cumulative (total)  
560 trauma score will be generated by assigning one-point for each of the following 15 traumas: **1)**  

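### After the amendments, women already at CES-D 16 or more can enter, yet the depression endpoint and its two-factor models still count their persisting scores as emerging episodes

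*Protocol*

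**What the plan says.** **Entry rule as designed.** The Brief Summary sets current symptoms at CES-D 8 or less. Inclusion Criteria lists "Current low level depressive symptoms (CES-D score" below 8, and the screening section says that a score of 9 or more "will result in exclusion and referral".

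**Entry rule as amended.** The list of amendments at the front of the Protocol says of "The requirement of having a baseline CES-D score" of 8 or less that the limit was raised to 16 or less (2010-11-16) "and later removed altogether" (2014-02-27).

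**Endpoint.** Affective Well-Being Measures defines a depression episode as CES-D of 16 or more, "and this cut-point has been used to define depressive episodes in multiple perimenopausal" samples. It places no condition on the baseline score.

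**Premise and model.** Aim 3 H2 begins "Although no subjects will be depressed at baseline, active treatment will be associated with" a lower proportion of women with episodes over 12 months. The Data Analytic Plan for that hypothesis specifies a logistic regression with two between-"subjects factors (DEP history and treatment) and the emergence of at least one DEP episode as" the response. Aim 2 H2 uses a two-factor logistic regression on the same endpoint. Randomisation is stratified on depression history only.

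**The concern.** The entry rule and the endpoint were built to fit together. With a ceiling of 8 and a cut-point of 16, any score at or above 16 during follow-up meant that the woman had worsened. The amendments removed that gap, and the endpoint and models were not revised to match.

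Two things are at stake.

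- **Meaning of the primary depression result.** Aim 3 H2 is the hypothesis on which the trial is powered, and the follow-on depression outcomes are tested only if it succeeds. If some events are women who were above the cut-point from the start, the comparison no longer measures prevention of new episodes alone.
- **Confounding in the non-randomised comparisons.** Aim 2 H2 compares women with and without a depression history within the placebo arm. Aim 1 H1 compares the same groups at baseline, and the Brief Summary says they were to be matched on low current symptoms. Without a limit on entry, a difference attributed to history may partly reflect current symptoms.

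**Working it through.** **1. Can a woman enter while already meeting the endpoint?**

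| Period | Baseline CES-D allowed | Overlap with the endpoint (16 or more) |
|---|---|---|
| Original | 8 or less | none |
| From 2010-11-16 | 16 or less | a score of exactly 16 |
| From 2014-02-27 | no limit | any score of 16 or more |

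Nothing downstream closes the overlap. The endpoint has no at-risk condition, the primary model has no baseline CES-D term, and randomisation is not stratified on it. Month 0 CES-D enters only the follow-on mixed model of CES-D scores.

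**2. The plan's own power figure.** Inputs from the power section: 18.75% (ERT) against 37.5% (placebo), two-sided 0.05, 240 women; 1:1 allocation gives n = 120 per arm. With d the difference in rates and p̄ their mean:

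Power = Φ{ (d − 1.96 √[2p̄(1−p̄)/n]) / √[(pE(1−pE) + pC(1−pC))/n] }

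= Φ{ (0.1875 − 1.96 × 0.0580) / 0.0568 } = 90.3%.

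The Protocol states more than 96%. The same formula gives 96.5% with the 320 randomised women. That mismatch is a separate matter. It matters here only because the reference for 240 women must be 90%, not 96%.

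**3. What women already at the cut-point do to the comparison.** Let f be the share starting at 16 or more, and qE and qC their chance of scoring 16 or more again on ERT and placebo. The documents give none of these, so all three are assumed. Each arm's rate becomes

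(1 − f) × p + f × q.

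With f = 20% and qC = 0.8, the placebo rate is 0.8 × 0.375 + 0.2 × 0.8 = 46%. On ERT, 0.8 × 0.1875 = 15% comes from women below 16, plus 0.2 × qE. With 240 women:

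| qE | ERT rate | Placebo rate | Risk ratio | Power, all women |
|---|---|---|---|---|
| 0.8 (no effect on persistence) | 31% | 46% | 0.67 | 67% |
| 0.6 | 27% | 46% | 0.59 | 87% |
| 0.4 (persistence halved) | 23% | 46% | 0.50 | 97% |

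References: 90% at f = 0, and 83% if the analysis is limited to women below 16 (192 of 240).

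With f = 10% and qC = 0.8, power is 80% at qE = 0.8 and 88% at qE = 0.6, against 87% when restricted (216 of 240).

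**4. Share of events that are not new.** At f = 20% and 0.8 persistence in both arms, women already at the cut-point supply 0.16/0.31 = 52% of ERT events and 0.16/0.46 = 35% of placebo events. At f = 10% the shares are 0.08/0.249 = 32% and 0.08/0.4175 = 19%.

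**The case against.** **Diagnosis is still screened.** The exclusion list bars "Current Axis I psychiatric diagnosis (e.g., depression, anxiety, substance" use and similar disorders, and candidates have a structured diagnostic interview. Taking that exclusion as still in force, the premise can hold by diagnosis. It does not hold by the definition that the endpoint uses, which is a score. The Protocol itself gives the cut-point a positive predictive value of 75%, so a woman can score 16 or more without a diagnosis.

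**Sensitivity analyses are promised.** General Statistical Considerations foresees adding confounders or moderators where appropriate. It does not name baseline CES-D there, and it leaves the primary test unchanged. A separate analysis plan might add the term, but this document already fixes the endpoint, the response and the model.

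**This is only an amendment list set against older text.** The Aim 3 H2 sentence was consistent when written, and a difference in wording would be no finding. What stands is that the later entry rule is the operative one, and the endpoint and model that depended on the old rule were not adapted.

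**The harm to power may not exist.** A reader might infer that women above the cut-point become events almost regardless of treatment, so that the effect must be diluted and power lost. The documents do not support that. Purpose and Rationale says ERT reduces symptoms in major, minor and subsyndromal depression, and the CES-D section calls elevated scores sensitive to ERT. If ERT lowers persistence, power can rise. This objection stands in full.

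**Exposure is limited.** Until 2014-02-27 only a score of exactly 16 overlapped, and enrolment after that date is not given. This also stands: f cannot be known from the document.

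**Restricting the primary set is not free.** It drops randomised women, sits badly with the stated intent-to-treat approach, and in some of the scenarios above has less power than counting everyone. This stands and shapes the fix.

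**Conclusion.** The point holds as a mismatch between the amended entry rule and an unamended endpoint and model. It should be fixed. It does not invalidate the trial: randomisation keeps the Aim 3 H2 test valid under the null.

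The firm part needs no assumption. As written, a persisting score counts as an emerging episode, so a treatment difference cannot be read as prevention of new episodes alone. Aim 2 H2 and Aim 1 H1 are open to confounding by current symptoms.

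The size is illustrative only. Across the persistence values tried at f = 20% and 240 women, power runs from 67% to 97% around a reference of 90%, so even the direction is uncertain. A claim that power is certainly lost, or that the primary set must be restricted, goes further than the document allows.

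**What to change.** - Keep all randomised women in the primary analysis, and add baseline CES-D as a pre-specified covariate to the Aim 3 H2 and Aim 2 H2 logistic models.
- Pre-specify, as a key supportive analysis, new onset: CES-D of 16 or more during follow-up in women below 16 at randomisation. Limit any claim about emergence to this analysis, because the covariate does not change what is counted as an event.
- Report Aim 1 H1 also adjusted for baseline CES-D, as a sensitivity analysis. It should not replace the unadjusted comparison, since current symptoms may be a consequence of the depression history and adjustment could remove part of the effect sought.
- Reword the Aim 3 H2 premise so that it no longer says without qualification that no woman is depressed at baseline. It can hold by diagnosis but not by the CES-D definition.

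The cost is slightly more analysis and some wording. Month 0 CES-D is already scheduled, so no new data are needed, and no randomised woman leaves the primary analysis.
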